After the previous procedure, an incision will be made in the gingival tissue around the tooth to be extracted, which will be gently moved away to expose the tooth neck. Then, with an atraumatic extraction kit, the dental element will be dislocated and, using forceps and/or an extractor, the element will be removed. Finally, a suture will be placed to bring the edges of the gingival tissue around the socket as close as possible.

From the dental element, the apical part of the element will be obtained together with the periodontal ligament, which will be immediately placed in individual bottles duly identified, containing 10% formalin solution, buffered with neutral pH, and stored for the first 20 hours and then washed in running water for another 12 hours to remove the fixing solution. After fixation, the pieces will be demineralized in a 10% EDTA solution28. Then, the pieces will be washed in running water, dehydrated in alcohol, cleared in xylene and embedded in paraffin. After inclusion, the pieces will be cut with semi-serial cuts, 3 µm thick, carried out using a microtome (Leica - RM 2045). For each specimen, 5 slides with 3 tissue sections will be prepared and stained with Hematoxylin-Eosin and Picrosirius red29.

Analysis of histological results

Analyzes will be performed at 400x magnification under light microscopy (DM 4000 B, Leica, Wetzlar, Germany) by a single, calibrated, and blinded operator. Histological analysis will be used to characterize the morphological structures of the periodontal ligament with the aim of identifying possible pathological changes. The results will be presented through descriptive and qualitative analysis. The analysis will consider: inflammatory infiltrate in terms of its intensity and extent; periodontal ligament organization; collagen fibers maturation; inflammatory and/or replacement resorption; and dental ankylosis. The two teeth used as controls will serve as baseline parameters to analyze possible morphological changes.

The inflammatory reaction will be scored according to the average number of inflammatory cells present in the middle third of the root of the teeth, being: Score 0, no or few cells (normal); Score 1, <25 cells (mild); Score 2, 25-125 cells (moderate); Score 3, >125 cells (severe).

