For the periodontal ligament organization analysis, the percentage of organization will be considered, where: Score 0, total organization (100%), Score 1, organization greater than 75% and less than 100%; Score 2, greater than 50% and less than 75%; and Score 3, organization of less than 50%.

Inflammatory and/or replacement resorption and dental ankylosis will be considered according to their intensity and extent, where: Score 0, absent, without the presence of the mentioned events; Score 1, change in an area less than 25%; Score 2, change in an area greater than 25% and less than 50%; Score 3, change in an area greater than 50%.

Statistical Analysis Plan

All statistical analysis will be performed using SigmaPlot 12.0[™] software (Chicago, IL, USA). The data obtained will be submitted to the Shapiro-Wilk normality test. Then, for comparisons between the Control and Treatment group, the Mann-Whitney U test will be used for nonparametric data. For parametric data, the Student t-test will be used. The level of significance will be set at 5%.

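### The inflammation score sets no count separating normal (Score 0) from mild (Score 1), and no counting unit, so the grade cannot be reproduced from the plan

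*Combined protocol and SAP*

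**What the plan says.** Analysis of histological results states that inflammation is "scored according to the average number of inflammatory cells present in the middle third of the root of the teeth". The two lowest grades are "Score 0, no or few cells (normal); Score 1, <25 cells (mild". Score 2 covers 25 to 125 cells and Score 3 more than 125. No number is attached to *few* anywhere in the document, and no rule says which grade prevails when two apply.

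The two percentage scales in the same section define their zero point exactly. Ligament organization begins with "Score 0, total organization (100" per cent, and resorption and ankylosis with "Score 0, absent, without the presence of the mentioned events".

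On the reading itself, the plan says "Analyzes will be performed at 400x magnification under light microscopy", "by a single, calibrated, and blinded operator". On reporting, it says "The results will be presented through descriptive and qualitative analysis". The two control teeth are to act as baseline parameters. The Statistical Analysis Plan adds a comparison of treatment with control: Shapiro-Wilk first, then Mann-Whitney or Student's t-test according to its outcome, at 5%. Study design and population gives at least ten treated teeth and two controls.

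**The concern.** The study is meant to show that the laser step leaves tissue outside the root undamaged, and inflammation is one of the features it examines. On this scale the line between normal and mild is the line between no finding and a finding. If the text does not fix that line, two competent readers could grade the same slides differently and both comply with the plan. Someone reading the results could not tell which cut-off had been used. Because results are to be presented descriptively, the grades are themselves the result, whatever a test says.

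**Working it through.** The documents give no expected counts, power or sample-size figure to reproduce. The check therefore sets the scoring rules against each other and then sizes the consequence.

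**1. Which grades each average count can receive**

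| Average count | Grades the wording admits |
|---|---|
| 0 | 0 (literally also 1, since 0 < 25) |
| Low non-zero, e.g. 1, 3, 5 | 0 or 1 |
| Higher, but below 25 | 1, and also 0 if the reader calls it few |
| 25 to 125 | 2 |
| Above 125 | 3 |

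Giving Score 0 precedence does not help, because *few* still has no end point. The range of sensible cut-offs is limited, though. A cut-off of 0 contradicts the wording, which admits some cells as normal. One just below 25 would leave the mild grade almost empty.

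**2. Counting unit.** The average has no stated denominator. It could be per field, per section or per area, and 400x is a magnification, not an area. Each specimen yields 5 slides with 3 sections. The limits 25 and 125 differ by a factor of 125/25 = 5. Tissue averaging just under 25 in one unit would therefore exceed 125 in a unit somewhat more than five times as large. The limits of Scores 2 and 3 meet cleanly, but they are fully determinate only once the unit is fixed.

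**3. Boundary percentages.** Organization of exactly 50% or 75%, and resorption or ankylosis of exactly 25% or 50%, falls between two strict inequalities and gets no score. This affects the severity grade only, not normal versus abnormal.

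**4. Descriptive size.** One tooth regraded between 0 and 1 moves the share called normal by 1/10 = 10 percentage points among treated teeth (less if more than ten are enrolled) and by 1/2 = 50 points among controls.

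**5. Effect on the test.** Take the exact permutation form of Mann-Whitney with mid-ranks, 10 versus 2, with C(12,2) = 66 allocations. The plan states neither that the test is exact nor which two-sided convention applies, so both are shown. Suppose scores are 0 and 1 only, both controls are at 0, and k treated teeth are at 1. The tail is then C(12−k, 2)/66.

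| k of 10 | Tail | p, distance from mean rank sum | p, doubled tail |
|---|---|---|---|
| 10 | 1/66 | 0.015 | 0.030 |
| 9 | 3/66 | 0.045 | 0.091 |
| 8 | 6/66 | 0.091 | 0.182 |

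With one control at Score 1, the smallest tail is 11/66, giving p = 0.167 or 0.333. With both controls at Score 1, the table is mirrored: no treated tooth at Score 1 gives 1/66. Only an extreme split reaches 5%.

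**6. Illustration with assumed counts (not trial data).** Let the controls average 2 and 3 cells and the treated teeth 6, 7, …, 15. Let K be the highest count called few. The p-values use the distance convention.

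| K | Treated at Score 1 | Controls at Score 1 | Exact p |
|---|---|---|---|
| 1 | 10 of 10 | 2 of 2 | 1.0 |
| 3 or 5 | 10 of 10 | 0 of 2 | 0.015 |
| 10 | 5 of 10 | 0 of 2 | 0.47 |
| 15 | 0 of 10 | 0 of 2 | 1.0 |

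The same test on the counts needs no K. Both controls rank lowest without ties, so p = 2/66 = 0.030.

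**The case against.** The strongest reply is that this is a wording gap that a calibrated reader will fill. One person reads every slide, blinded, so whatever *few* means should be applied alike in both groups. Inflammation is one of five listed features, none is named primary, and the plan does not promise a count of normal teeth. Much of this stands: the reading arrangements limit differential bias, and the issue is confined to low counts on one scale. But calibration to an unwritten standard does not let anyone else reproduce the grade. The control teeth do not supply the standard either, since they are graded on the same scale and are not said to define *few*.

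A reader might infer three stronger things that the documents do not support.

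- *The gap favours the no-damage conclusion, because a lenient cut-off makes more teeth normal.* Leniency would act on both groups. A strict cut-off can also remove any difference between them: in the illustration, K = 1 and K = 15 both give p = 1.0. No direction is shown.
- *Any cut-off from 0 to just below 25 is open.* Neither end sensibly fits a four-grade scale whose lowest grade allows a few cells.
- *The gap will decide significance.* That needs an extreme split, and the documents give no counts from which to judge whether one is likely.

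**Conclusion.** The concern holds in limited form. The normal/mild grade depends on an unwritten cut-off lying above 0 and well below 25, the averaging unit is unstated, and four boundary percentages have no score. The cost is reproducibility and precision, with no demonstrated bias. Descriptively it is worth up to 10 points per treated tooth and 50 points per control tooth in the ambiguous band, assuming ten treated teeth. The number of such teeth and the effect on any p-value are unknown.

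It would also be too strong to say that averages of 25 or more are graded beyond doubt, since that holds only after a counting unit is set.

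The plan should be changed because a better measure is already to hand. The average count has to be obtained in order to assign the score, and analysing it removes the arbitrary cut and most ties.

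**What to change.** - Record and report the average inflammatory cell count for each tooth. Fix the field or area counted, and the number of fields averaged, before any slide is read. Without this, neither the count nor a new cut-off is reproducible.
- Use that count, instead of the 0–3 score, as the inflammation value compared between groups, by Mann-Whitney. State this as a change to the Statistical Analysis Plan, which now chooses between Mann-Whitney and the t-test after Shapiro-Wilk. A normality check on two controls is uninformative. State also whether the test is exact and which two-sided convention applies.
- Keep the 0–3 score as descriptive. Set a numeric upper count for Score 0 before reading, and let Score 1 run from above that count to below 25. The documents do not supply the number, so the investigators must choose and justify it.
- Assign 50% and 75% organization, and 25% and 50% resorption or ankylosis, to one score each.

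The cost is one data-sheet column and a few words. This assumes that the middle third of the root, where cells are to be counted, is on the prepared sections. Tooth extraction and histotechnical processing says that "the apical part of the element will be obtained together with the periodontal ligament", and the two statements must be reconciled. None of this makes a comparison of 10 teeth with 2 able to establish absence of risk.

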Histopathological Evaluation of the Periodontal Ligament and Cementum of Extracted Teeth Subjected to Laser Ablation with Indocyanine Green

Device Investigated: Leonardo Diode Laser with the LEAP Laser Absorption Solution

Indication Studied: Pulpectomy. Specifically, a laser ablation step facilitated with the LEAP solution, added to the standard procedure for tooth pulpectomy, does not present a risk of damage to tissues and structures external of the treated root as a consequence of possible temperature increases.

Sponsor: CAO Group, Inc.

Protocol ID: 70009423.2.0000.5539

Development Phase: Performance Validation

NCT ID: Not Yet Assigned

Anticipated Initiation Date: 1 August 2023

Anticipated Completion Date: 30 September 2023

Document Date: 10 July 2023

DATA COLLECTION INSTRUMENT

Clinical Procedures and Sample Collection

Study design and population

The patients will be treated at the Unicesumar Dental Clinic. Ten healthy female and male patients, over 18 years old, and in need of tooth extraction, will be selected for the study. Patient selection will be carried out through anamnesis and clinical/imaginological examinations. The inclusion criterion are: lower incisors with indication for extraction.

The exclusion criteria are: other dental groups; teeth that have periodontal disease beyond the apical third of the root; and teeth that do not require tooth extraction.

At least ten teeth will be included in this study for the treatment group, and two other teeth will be used as a control group. The study is porposed under submission to the Human Research Ethics Committee (CAAE 70009423.2.0000.5539) and all patients who agreed to participate in the research will sign the Informed Consent Form.

Endodontic treatment procedure

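### The SAP should name the average inflammatory cell count, rather than its four-band grade, as the variable tested; if the grade is tested, a three-fold rise lying largely within one band is usually missed

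*Combined protocol and SAP*

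**What the plan says.** Under *Analysis of histological results*, the inflammatory reaction is "scored according to the average number of inflammatory cells present in the middle third of the root of the teeth", with the bands "Score 1, <25 cells (mild); Score 2, 25-125 cells (moderate); Score 3, >125 cells (severe". Score 0 is described as no or few cells, with no number for *few*. Ligament organisation is graded from a percentage: "Score 0, total organization (100%), Score 1, organization greater than 75% and less than 100", and so on down. Resorption and ankylosis are graded from the proportion of area changed: "Score 1, change in an area less than 25%; Score 2, change in an area greater than 25% and less than 50", and so on up.

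Under *Study design and population*: "At least ten teeth will be included in this study for the treatment group, and two other teeth will be used as a control group".

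Under *Statistical Analysis Plan*, the text begins "The data obtained will be submitted to the Shapiro-Wilk normality test" and continues "for comparisons between the Control and Treatment group, the Mann-Whitney U test will be used for nonparametric data", with a Student t-test for parametric data and a 5% significance level. It does not say whether the data are the counts and percentages or the grades, and it defines no analysis of the underlying values.

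**The concern.** To place a tooth in Score 1, 2 or 3 for inflammation, the reader must set an average count against limits of 25 and 125. The count therefore exists, or nearly exists, before the grade does. If only the grade goes into the comparison, any difference inside a band is discarded, and the ties it creates weaken a rank test that has just two teeth on one side.

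The direction of the loss matters. The indication on the title page is that the added laser step carries no risk of damage to tissues outside the root. A finding of no difference is the favourable result, so an insensitive comparison helps the claim.

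**Working it through.** **Inputs from the documents.** Ten treated teeth (the stated minimum) and two controls; cut-points of 25 and 125 cells; 5% significance level. The plan states no power, effect size or variance, so it has no figure to reproduce.

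**Assumptions.** Two-sided test; lognormal counts; treated median three times the control median; between-tooth log-SD of 0.3, 0.5 or 0.7; *few* taken as under 5 cells.

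**1. Band width.** Score 2 spans 125/25 = 5-fold. Since 125/3 = 41.7, any control count from 25 to 41 can triple and stay in Score 2.

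**2. What the test needs.** There are C(12,2) = 66 ways to choose the two controls. On untied counts, only complete separation is significant: p = 2/66 = 0.030, and the next possible value is 4/66 = 0.061. On grades, suppose both controls share a grade and k of the ten treated teeth are one grade higher. Then p = C(12−k, 2)/66 for these large k:
- k = 10: 1/66 = 0.015
- k = 9: 3/66 = 0.045
- k = 8: 6/66 = 0.091

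Two treated teeth left in the controls' grade are enough to lose significance. If all 12 teeth share a grade, p = 1. As an example, controls at 30 and 33 cells with ten treated teeth between 90 and 110 give exact p = 0.030 on counts and p = 1 on grades.

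**3. Simulated power.** Exact two-sided Mann-Whitney, all 66 allocations enumerated, midranks for ties, 2,000 to 6,000 trials per setting (Monte Carlo standard error at most √(0.25/2000) = 1.1 points).

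| Control to treated median | log-SD | Counts | Grades |
|---|---|---|---|
| 30 to 90 | 0.3 | 94% | 8% |
| 30 to 90 | 0.5 | 54% | 12% |
| 30 to 90 | 0.7 | 31% | 13% |
| 15 to 45 | 0.3 | 94% | 89% |
| 15 to 45 | 0.5 | 55% | 48% |

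**4. Hand check of the graded figures at log-SD 0.3.**
- *30 to 90.* Nearly the only route to significance is both controls falling below 25. P(control < 25) = Φ(ln(25/30)/0.3) = Φ(−0.61) = 0.272, and 0.272² = 0.074, close to the simulated 8%.
- *15 to 45.* P(control < 25) = Φ(ln(25/15)/0.3) = Φ(1.70) = 0.956, and 0.956² = 0.914. P(treated > 25) = Φ(ln(45/25)/0.3) = Φ(1.96) = 0.975. P(at least nine of ten above 25) = 0.975¹⁰ + 10 × 0.025 × 0.975⁹ = 0.776 + 0.199 = 0.975. The product is 0.914 × 0.975 = 0.89, as simulated.

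**5. How often all 12 teeth share Score 2 (30 to 90).** At log-SD 0.3, P(control in band) = 0.728 and P(treated in band) = 0.863, so the chance is 0.728² × 0.863¹⁰ = 12%. At 0.5 it is 0.640² × 0.739¹⁰ = 2%.

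**6. Averaged over baselines.** With control medians spread log-uniformly from 2 to 125 cells and a three-fold rise, exact power is 94% on counts v 44% on grades at CV 30%, and 59% v 28% at CV 50%. CV converts to log-SD by √ln(1 + CV²): 30% is 0.29 and 50% is 0.47.

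**7. Dependence on *few*.** For 8 to 24 cells at log-SD 0.5, graded power is about 0.4%, 4% or 42% if *few* means under 2, under 5 or under 10. Power on counts is about 54% whichever is meant.

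**The case against.** **The SAP never says that grades are tested.** This stands. A normality check with a t-test branch fits raw counts at least as well as 0-3 grades. A reader might infer that the plan commits itself to testing grades; it does not. It leaves the variable unnamed, and the grade is only the likeliest candidate because nothing else is defined.

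**The worst case is not the typical case.** A reader might infer that a three-fold rise would generally leave every tooth in one grade and the test blind. The documents do not support that. They give no baseline count or spread; all 12 teeth share a grade in at most about 12% of trials in the 30 to 90 scenario; and the loss nearly vanishes when the rise straddles a cut-point. The low graded power comes mainly from partial overlap combined with only two controls.

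**The exact test is itself an assumption.** The SAP names Mann-Whitney in a software package without specifying exact p-values. Under a tie-corrected normal approximation the average graded power at CV 30% rises from 44% to 64%, and in some cut-crossing cases grades match or beat counts (15 to 45 cells, CV 30%: 98% v 94%). The within-band loss remains: 30 to 90 cells at CV 30% gives 94% on counts and 16% on grades.

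**Percentages differ from counts.** This stands. The plan describes a single operator at a light microscope and no morphometry, so organisation and area bands may be assigned by eye. A reader might infer that percentages could be tested at no cost; the documents do not show that a usable number exists.

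**The test is not the sole basis for the conclusion.** The plan also says that results will be presented descriptively and qualitatively. That softens the consequence but does not justify discarding a count already made.

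**Conclusion.** The concern holds for the cell count. The plan bands a count into four wide grades and does not say which of the two is tested. If it is the grade, a three-fold rise lying largely within Score 2 is detected with about 8-13% power, against 31-94% on counts. The loss is a few points when the rise crosses a cut-point, and roughly half the power on average over the baselines examined with the exact test.

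These sizes rest on assumed lognormal counts, baselines and log-SDs, on the exact two-sided test, and on the inference that grades are what is compared. That the loss within a band can be near-total follows from the plan's own cut-points. For percent organisation and percent area, the same mechanism applies only if the reader actually produces a percentage.

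Testing counts does not repair the two-tooth control group. Complete separation is still required for significance, and power on counts is only 31% at log-SD 0.7.

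**What to change.** In the SAP:
- Name the per-tooth average inflammatory cell count as the variable compared between groups, using the exact Mann-Whitney test.
- Have the blinded reader record that count beside the grade.
- Keep the 0-3 scores as a descriptive table. The comparison then no longer depends on what *few* means.
- For percent organisation and percent area, record and test the percentage only if the reader already estimates a number; otherwise keep the grades and say that the grade is what is tested.

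The cost is a sentence or two in the SAP and one more column on the reading sheet. For cell counts no extra teeth, slides or readings are needed.

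### The Shapiro-Wilk step leaves the choice between t-test and Mann-Whitney open for 0-3 scores; one pre-specified exact rank test on one value per tooth would settle it cheaply

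*Combined protocol and SAP*

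**What the plan says.** The Statistical Analysis Plan is one paragraph. It states "The data obtained will be submitted to the Shapiro-Wilk normality test", then that "the Mann-Whitney U test will be used for nonparametric data" and "For parametric data, the Student t-test will be used". The significance level is 5%. The software is SigmaPlot 12.0, with no settings given.

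Under Study design and population, at least ten teeth are treated and "two other teeth will be used as a control group".

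Every outcome given a scoring rule is graded 0 to 3. For inflammation, "The inflammatory reaction will be scored according to the average number of inflammatory cells present in the middle third of the root". For ligament organization, "the percentage of organization will be considered" and then classed. Resorption and ankylosis are classed by affected area.

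On sampling within a tooth, "For each specimen, 5 slides with 3 tissue sections will be prepared". On reporting, the section Analysis of histological results says "The results will be presented through descriptive and qualitative analysis".

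**The concern.** The plan does not say whether the normality test is applied to the scores or to the counts and percentages behind them. Nor does it say whether it is applied to each group, to all teeth pooled or to residuals, or what happens if it cannot be computed. No wording keeps four-class scores out of the t-test. The Mann-Whitney test is named without its form (exact or normal approximation), a tie rule or sidedness.

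The test, and for some score sets the 5% verdict, could therefore be settled only after the slides are read. The study is meant to support a statement that the laser step does no harm outside the root, so a p-value from 10 v 2 teeth may be read as safety evidence. The test behind it should be fixed in advance.

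**Working it through.** **Inputs.** From the documents: 10 treated teeth (the stated minimum), 2 control teeth, scores 0-3, 5% level. Assumed: one score per tooth, two-sided tests, and a 5% level for the normality test too. The plan states no power or sample-size figure, so there is none to reproduce.

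**1. Can the gate run?** Shapiro-Wilk needs at least three values. On two it returns no result. On the 12 pooled scores or the 12 within-group residuals it does run.

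**2. How often does the choice of tested values matter?** There are C(13,3) = 286 sets of ten four-class scores; 286 − 4 constant sets = 282. The sets are not equally likely, so these counts are not probabilities.
- Controls 0,0: the gate sends 35 sets (treated arm tested), 29 (pooled) or 43 (residuals) to the t-test. The route differs between the three readings in 46 sets. The 5% verdict, with exact Mann-Whitney on the rank branch, differs in 1.
- The verdict differs in 7 sets for controls 0,1, in 1 for controls 0,2, and in none for 1,1 or 1,2.

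The chance that the treated-arm gate changes the verdict, compared with exact Mann-Whitney throughout, is 0.80% for class probabilities .25 each and 0.20% for .1/.4/.4/.1, if both arms share the distribution. It is 6.4% and 9.9% only if both controls score 0.

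**3. A set where the verdict does change.** Treated 1,1,1,2,2,2,2,3,3,3; controls 0,1.
- Shapiro-Wilk p: treated arm 0.035 (to Mann-Whitney); pooled 0.134 and residuals 0.081 (to t).
- t-test: means 2.0 and 0.5; pooled variance (6 + 0.5)/10 = 0.65; t = 1.5/√(0.65 × (1/10 + 1/2)) = 2.40 on 10 df; p = 0.037.
- Exact Mann-Whitney: midranks are 1 (score 0), 3.5 (score 1), 7.5 (score 2) and 11 (score 3). The control rank sum is 4.5 against a mean of 13. At least as far from 13 are 4 allocations in the lower tail and 3 in the upper, so p = 7/66 = 0.106 (doubled tail 8/66 = 0.121). The normal approximation gives 0.056, or 0.073 with continuity correction.

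**4. Scores piled at 0.** Treated all 0; controls 0,1. The pooled and residual gates both reject normality, and the treated arm has no variation to test. So the form of Mann-Whitney is what matters.
- Midranks: 6 for the eleven 0s, 12 for the single 1. Control rank sum 18, deviation 18 − 13 = 5.
- Exact: the tooth scoring 1 falls in the control pair in 11 of 66 allocations; p = 11/66 = 0.167.
- Approximation: variance (20/12) × [13 − (11³ − 11)/132] = 5; z = 5/√5 = 2.236, p = 0.025. With continuity correction, z = 4.5/√5 = 2.012, p = 0.044.

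Here one abnormal control tooth would make treatment look significantly better.

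**5. Error rate for such scores.** With both arms at assumed class probabilities .8/.15/.05/0, enumeration gives a two-sided Mann-Whitney size of 6.0% uncorrected, 5.7% corrected and 1.9% exact. The pattern in step 4, including a control score of 2 instead of 1, has probability 0.8¹⁰ × 2 × 0.8 × 0.2 = 3.4% and accounts for most of the first two.

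**The case against.** The strongest reply is that this hardly affects the study. Results are mainly descriptive and qualitative, and the gate seldom changes the verdict. In the example of step 3 every treated tooth is abnormal, so p=0.037 or 0.106 would scarcely alter the reading. That stands, and it limits the point to a cheap improvement.

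The phrase about nonparametric data may be meant to cover ordinal scores, with the t-test kept for counts or percentages. That is possible, but the text does not say it.

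The per-tooth value is partly settled. For inflammation, scoring an average cell count already points to one class per tooth. That stands for inflammation; the other scores have no such rule. A reader might infer from 15 sections per tooth that sections would be analysed, as 30 v 150 values. The documents do not say that, nor how the sections are shared between the two stains.

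Naming the software may fix the Mann-Whitney form through a default. The documents do not show what that default is, so it cannot be said that the form is chosen after the data, nor that it is known.

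A reader might also infer that the plan cannot be executed. It can: the gate fails only when run on the control group alone with one value per tooth.

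**Conclusion.** The concern holds in a limited form. The gate does not identify the values it tests, cannot be computed on the two control teeth alone with one value each, and as written can send 0-3 scores to a t-test. It changes the route more often than the conclusion: 46 sets against 1 of 282 with controls 0,0, and at most 7 verdicts for the other control pairs examined.

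A reader might infer that the gate inflates the false-positive rate. The figures do not support that. With exact p-values on the rank branch, the size of the gated rule was 0.55% to 3.5% over five assumed score distributions and three readings of the gate. The excess over 5% in step 5 belongs to the normal approximation for scores piled at 0. It is small (6.0% or 5.7%) and rests on assumed class probabilities. Whether it would arise here depends on what SigmaPlot 12.0 does.

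All figures assume exactly ten treated teeth and one score per tooth. They also treat teeth as exchangeable. That is an assumption: no random allocation of controls is described, and with ten patients planned and at least twelve teeth, a patient may supply more than one.

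**What to change.** For the 0-3 scores, delete the Shapiro-Wilk step and the t-test, and state before any slide is read:
- one two-sided exact permutation Mann-Whitney test with midranks for ties, and one definition of the two-sided p;
- p taken over all C(n+2, 2) allocations for the n treated teeth actually included: 66 for n = 10, 78 for n = 11;
- one value per tooth: for inflammation the class of the average cell count, as the scoring rule already implies; for the other scores, a rule of the team's choice;
- that the test treats teeth as exchangeable, and why this is an assumption;
- software confirmed to run the exact test with ties.

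Report every tooth's scores, and state that non-significance at about 10 v 2 is not evidence of no damage.

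The cost is one SAP paragraph and no new data. The downsides are that the t-test's nominal sensitivity is given up, the exact test is conservative (1.9% in step 5), and other software may be needed. The comparison stays weak: without ties, the smallest two-sided exact p at 10 v 2 is 2/66 = 0.030, so significance needs complete or nearly complete separation.

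### The only planned inference is a 5% difference test of at least ten treated against two control teeth; a non-significant result could not support the statement that the laser step carries no risk of damage

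*Combined protocol and SAP*

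**What the plan says.** All references are to the combined protocol and SAP.

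- **Indication Studied** states that the laser step, added to standard pulpectomy, "does not present a risk of damage to tissues and structures external of the treated root as a consequence of possible temperature increases". This is an absence-of-harm statement.
- **Study design and population** gives the sizes: "At least ten teeth will be included in this study for the treatment group, and two other teeth will be used as a control group". It plans "Ten healthy female and male patients, over 18 years old" and does not say whether those ten patients supply all the teeth.
- **Analysis of histological results** provides for a single blinded reader and 0–3 scores. "The results will be presented through descriptive and qualitative analysis". On the controls: "The two teeth used as controls will serve as baseline parameters to analyze possible morphological changes".
- **Statistical Analysis Plan** is one short paragraph. A Shapiro-Wilk test selects the comparison: "for comparisons between the Control and Treatment group, the Mann-Whitney U test will be used for nonparametric data", and Student's t-test for parametric data, at 5%.

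No section gives a confidence interval, a margin, an acceptable rate of change, a success criterion or a reason for the sample size. Sidedness, exact or approximate p-values, and the unit of analysis are not stated.

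**The concern.** A difference test can give evidence that the groups differ. When it is not significant, it does not show that they are the same, least of all with two controls. Here the statement of interest is that harm is absent, and the difference test is the only inferential result the plan will produce. The report could therefore carry a finding of no significant difference on an outcome where most treated teeth show change, with no planned interval or rule to set against the no-risk statement. The scores could give an honest upper bound on the rate of change, but the plan does not ask for one.

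**Working it through.** The plan states no power, effect size or margin, so there is no figure of its own to reproduce. Instead, the check asks what the planned test would report under plain outcomes.

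**Inputs.** From the documents: 10 treated and 2 control teeth (the stated minimum), scores 0–3, 5% level. Assumed: one score per tooth, independent teeth, a two-sided test, both controls at 0.

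**Seven of ten affected, all at one score.** Five teeth are at 0 (three treated, two control) and seven are tied above.

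- Exact: both controls fall among the five zeros with probability C(5,2)/C(12,2) = 10/66 = 0.152. Doubling the tail gives 0.303.
- Normal approximation: U = 7×2 + 3×2×0.5 = 17, with mean 10×2/2 = 10. Tie-corrected variance = (20/12)×[13 − (120 + 336)/132] = 15.91, SD 3.989. z = 7/3.989 = 1.755, p = 0.079. With continuity correction, z = 6.5/3.989 = 1.630, p = 0.103.
- t-test: means 0.7 and 0; pooled variance = 10×0.7×0.3/10 = 0.21; SE = √[0.21×(1/10 + 1/2)] = 0.355; t = 1.97 on 10 df, p = 0.077.

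Putting all seven at Score 3 multiplies the mean and SE by 3 and leaves the ranks alone, so every p is unchanged.

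| Affected, one shared score | Exact, by distance | Exact, doubled | Normal, corrected | Normal, uncorrected | t-test |
|---|---|---|---|---|---|
| 7 of 10 | 0.152 | 0.303 | 0.103 | 0.079 | 0.077 |
| 8 of 10 | 0.091 | 0.182 | 0.049 | 0.036 | 0.027 |
| 9 of 10 | 0.045 | 0.091 | 0.015 | 0.010 | 0.003 |

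**Mixed severity.** Seven affected teeth can be spread over scores 1 to 3 in C(9,2) = 36 ways. Over all 36, the smallest p is 0.079 (Mann-Whitney) and 0.077 (t-test). Eight affected teeth give C(10,2) = 45 ways, of which 31 are non-significant by every variant in the table. When all eight share one score, the result depends on the method (Mann-Whitney 0.036 to 0.18).

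**The normality step.** At 7 of 10, where Shapiro-Wilk would select the t-test, p runs from 0.114 to 0.181 (8 mixes, tested on treated teeth) or from 0.107 to 0.163 (10 mixes, tested on residuals). No mix passes on pooled scores.

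**Other readings of the plan.** With 12 v 2, 8 of 12 affected is non-significant at every mix (smallest p 0.089). With a one-sided test and one shared Mann-Whitney score, 7 of 10 depends on the method (0.040 to 0.152) and 6 of 10 is non-significant (0.069 to 0.227).

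**What clean data would show.** The exact upper limit for 0 of n is 1 − a^(1/n).

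- 0/10: 1 − 0.025^(1/10) = 30.8% two-sided; 1 − 0.05^(1/10) = 25.9% one-sided.
- 0/2 controls: 1 − 0.025^(1/2) = 84% two-sided.

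**The case against.** The strongest reply is that histology is meant to be read descriptively. A blinded reader looks for pathological change, and seven severely changed teeth would be visible in that account whatever the p-value. This is right, and the point does not depend on anyone overlooking them. But the descriptive reading has no criterion for concluding that there is no damage, so it does not supply the missing rule.

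A reader might infer that the plan equates non-significance with safety. It does not say so. What can be said is that its only inferential result could not support the statement.

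A reader might also infer that ties are certain and that 7 of 10 must be non-significant. That holds only if one 0–3 score per tooth is tested, and the SAP does not say what is tested.

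- On raw cell counts the result can differ. For example, take assumed controls of 0 and 1 cells, three treated teeth at 2, 3 and 4, and seven at 30 to 150. The groups separate completely and the exact Mann-Whitney p is 2/66 = 0.030.
- If each of the 15 sections per specimen (5 slides × 3) were treated as independent, the comparison would be 150 v 30. Seven of ten affected teeth would then give p < 0.001, through pseudoreplication.

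These alternatives change the illustration. They do not make a non-significant difference test evidence of no risk.

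Nor does the verdict at 8 of 10 always turn on the p-value method: with mixed severity, most patterns are non-significant by every method.

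**Conclusion.** The point stands and should be settled before analysis. The no-risk statement has no interval, margin or rule behind it, and a non-significant test of at least ten against two teeth could not support it. That conclusion is logical and needs no assumption about the data. The 7-of-10 and 8-of-10 figures illustrate its size, and rest on tooth-level scores, independent teeth, 10 v 2, two-sided testing and clean controls. The limits of 30.8% for 0/10 and 84% for 0/2 also assume independent teeth. They show that even the best possible result would leave a substantial rate of change open in treated teeth and say almost nothing about the background rate.

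**What to change.** 1. Do not base the conclusion on the difference test. Label p-values descriptive, and state that non-significance is not evidence of no risk.
2. Make the tooth the unit, or the patient if one patient supplies several treated teeth. State how the 15 sections per specimen give one score.
3. For each scored outcome, report the number of treated teeth with change and an exact (Clopper-Pearson) 95% interval, stated as one- or two-sided. Show both control scores beside it. For inflammation, count Score 2 or higher unless the two lowest levels, which overlap, are first separated: "Score 0, no or few cells (normal); Score 1, <25 cells (mild".
4. Limit the Indication Studied statement to the observed count and its upper limit, for change from any cause visible at extraction. Two controls cannot isolate laser heat. If a yes/no safety conclusion is wanted, the sponsor must state in advance the largest acceptable rate, to be compared with the upper limit.

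**Cost.** A less favourable stated conclusion and a little more analysis; no extra patients or procedures. The change does not make a heat-specific statement supportable.

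**Separate from this point.** Some boundary values have no score, and collagen maturation is listed as an outcome without a scale. The protocol also keeps the apical part of the tooth but scores inflammation in the middle third of the root. Those two passages must be reconciled before the inflammation count can be relied on.
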